8.2.5 Clinical Safety Laboratory Assessments

See [Appendix 2](#) for the list of clinical laboratory tests to be performed and to the schedule of activities (see Section [1.3](#)) for the timing and frequency.

The investigator must review the laboratory report, document this review, and record any clinically relevant changes occurring during the study in the Adverse Event eCRF. The laboratory reports must be filed with the source documents. Clinically significant abnormal laboratory findings are those that are not associated with the underlying disease, unless judged by the investigator to be more severe than expected for the participant's condition. A laboratory test result must be reported as an adverse event if it meets any of the following criteria:

- Is accompanied by clinical symptoms
- Results in a change in study treatment (e.g., dosage modification, treatment interruption, or treatment discontinuation)
- Results in a medical intervention (e.g., potassium supplementation for hypokalemia) or a change in concomitant therapy
- Is clinically significant in the investigator's judgment

Medical and scientific judgment should be exercised in deciding whether an isolated laboratory abnormality should be classified as an adverse event.

All laboratory tests with values considered clinically significantly abnormal during participation in the study or within 14 days *of the final* dose of study treatment should be repeated until the values return to normal or baseline or are *considered to be stable and* no longer considered clinically significant by the investigator. If such values do not return to normal or baseline within a period of time judged reasonable by the investigator, the etiology should be identified and the Sponsor notified.

All protocol-required laboratory assessments, as defined in [Appendix 2](#), must be conducted in accordance with the laboratory manual and the schedule of activities (Section [1.3](#)).

If laboratory values from non-protocol-specified laboratory assessments performed at the institution's local laboratory require a change in participant management or are considered clinically significant by the investigator (e.g., serious adverse event or adverse event or dose modification), the results must be recorded on the eCRF.

Samples collected for safety laboratory tests will be destroyed no later than the time of completion of the final CSR.

8.2.6 Pregnancy Testing

The schedule for pregnancy testing for enrolled female participants is outlined in Section [1.3](#) and will be conducted as outlined in [Appendix 2](#).

8.2.7 Monitoring for Suicidal Ideation and Behavior

The assessment for suicidality in clinical trials is a requirement for CNS-active molecules requested by health authorities.

The C-SSRS is a clinician-rated tool recommended by health authorities, including the FDA, to assess previous suicidality of a subject (C-SSRS Baseline/Screening version) as well as any new instances of suicidality during this study (C-SSRS Since Last Visit version to be used at subsequent visits) (Posner et al. 2009a, Posner et al. 2009a) ([Appendix 11](#)). The C-SSRS incorporates a structured interview to prompt recollection of suicidal ideation, including the intensity of the ideation, behavior, and attempts with actual/potential lethality.

The C-SSRS is made up of ten categories, all of which maintain binary responses (yes/no) to indicate a presence or absence of the behavior. The ten categories included in the C-SSRS are as follows: Category 1-Wish to be Dead; Category 2-Non-specific Active Suicidal Thoughts; Category 3-Active Suicidal Ideation with Any Methods (Not Plan) without Intent to Act; Category 4-Active Suicidal Ideation with Some Intent to Act, without Specific Plan; Category 5-Active Suicidal Ideation with Specific Plan and Intent; Category 6-Preparatory Acts or Behavior; Category 7-Aborted Attempt; Category 8-Interrupted Attempt; Category 9-Actual Attempt (non-fatal); Category 10-Completed Suicide. A yes or no binary response is also utilized in assessing self-injurious behavior without suicidal intent. The outcome of the C-SSRS is a numerical score obtained from the aforementioned categories. The maximum suicidal ideation category (1–5 on the C-SSRS) will determine the suicidal ideation score for the participant. A score of 0 represents no ideation.

Participants should be monitored appropriately and observed closely for suicidal ideation and behavior or any other unusual changes in behavior. Consideration should be given to discontinuing the study drug in participants who experience signs of suicidal ideation or behavior, following a risk assessment. If the investigator concludes there is a risk of suicidality for a participant, the investigator must further evaluate the risk, which may involve local experts in the field of suicidality.

8.3 ADVERSE EVENTS, SERIOUS ADVERSE EVENTS, AND OTHER SAFETY REPORTING

The definitions of adverse event and serious adverse event can be found in (see Sections [A3–1](#) and [A3–2](#)).

Adverse events will be reported by the participant (or, when appropriate, by a caregiver, surrogate, or the participant's legally authorized representative).

The investigator and any qualified designees are responsible for detecting, documenting, and recording events that meet the definition of an adverse event or serious adverse event and remain responsible for following up adverse events that are serious, are

considered related to the study treatment or study procedures, or caused the participant to discontinue the study treatment (see Section 7).

8.3.1 Time Period and Frequency for Collecting Adverse Event and Serious Adverse Event Information

After informed consent has been obtained but prior to initiation of study drug, only serious adverse events caused by a protocol-mandated intervention should be reported. The paper Clinical Trial Adverse Event/Special Situations Form provided to investigators should be completed and submitted to the Sponsor or its designee immediately (i.e., no more than 24 hours after learning of the event), either by faxing or by scanning and emailing the form using the fax number or email address provided to investigators. All other medical occurrences that begin before the start of study treatment but after obtaining informed consent will be recorded on the General Medical History and Baseline Conditions eCRF, not the Adverse Event eCRF.

All adverse events will be reported from the start of treatment until 14 days after final study drug or until the last follow-up visit at the timepoints specified in the schedule of activities (see Section 1.3).

All serious adverse events will be recorded and reported to the Sponsor or designee immediately and under no circumstance should this exceed 24 hours, as indicated in [Appendix 3](#). The investigator will submit any updated serious adverse event data to the Sponsor within 24 hours of it being available.

Investigators are not obligated to actively seek adverse event or serious adverse event information after conclusion of study participation. However, if the investigator learns of any serious adverse event, including a death, at any time after a participant has been discharged from the study, and he or she considers the event to be reasonably related to the study treatment or study participation, the investigator must promptly notify the Sponsor.

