1.3 SCHEDULE OF ACTIVITIES

Table 1 Schedule of Activities

	Screening	Pre-Rand. Visit	Blinded Treatment Period						Safety Follow-Up ^a	Early Discont. ^{b, c}
Week			0	2	4 ^d	6	9 ^d	12	14	
Study Day(s)	-28 to -1	-7 to -1	1	14	28	42	63	84	98	
Visit window (days)				±3	±3	±3	±3	±3	-3/+7	
Informed consent ^e	x									
Medical history, demographics, and baseline conditions ^f	x									
Resting-state EEG ^g		x ^h		x		x		x		x ⁱ
Urinalysis ^j	x								x	x
Urinalysis for substance abuse ^k	x		x			x		x	x	x
Serology (HIV, and hepatitis B and C) ^l	x									
Coagulation ^m	x							x		x
Pregnancy test ⁿ	x		x			x		x		x
Weight and height (height to be measured at screening only)	x							x		x
Vital signs ^o	x		x	x		x		x	x	x
PK blood sample ^p				x		x		x		x
Clinical genotyping sample ^q			x							
Blood sample for WGS ^r			x							
RBR blood sample (optional) ^s				x						

Table 1 Schedule of Activities (cont.)

	Screening	Pre-Rand. Visit	Blinded Treatment Period						Safety Follow-Up ^a	Early Discont. ^{b, c}
Week			0	2	4 ^d	6	9 ^d	12	14	
Study Day(s)	-28 to -1	-7 to -1	1	14	28	42	63	84	98	
Visit window (days)				±3	±3	±3	±3	±3	-3/+7	
Complete physical examination ^t	x		x					x	x	x
Limited physical examination ^t						x				
Neurologic evaluation (upper and lower limbs)	x		x			x		x	x	x
Clinical signs and symptoms of infection ^u					x	x	x	x		
12-Lead ECG ^v	x		x	x				x	x	x
Hematology ^w	x		x			x		x	x	x
Full serum chemistry ^x	x		x			x		x	x	x
Quantitative immunoglobulins (IgA, IgG, IgM, and IgE)			x					x		x
PCL-5	x		x	x		x		x		x
SCID-5	x									
LEC-5	x									
CAPS-5 (administered by central rater)		x ^h				x		x		x
CGI-S			x			x		x		x
CGI-C						x		x		x
PGI-S			x			x		x		x
PGI-C						x		x		x

Table 1 Schedule of Activities (cont.)

	Screening	Pre-Rand. Visit	Blinded Treatment Period						Safety Follow-Up ^a	Early Discont. ^{b, c}
Week			0	2	4 ^d	6	9 ^d	12	14	
Study Day(s)	-28 to -1	-7 to -1	1	14	28	42	63	84	98	
Visit window (days)				±3	±3	±3	±3	±3	-3/+7	
Beck Anxiety Inventory			x			x		x		
Pittsburgh Sleep Quality Index			x			x		x		
PHQ-9			x			x		x		x
C-SSRS ^y	x	x	x	x	x	x	x	x	x	x
SDS			x			x		x		
CPFQ			x			x		x		
Computerized cognitive battery		x ^h		x		x		x		x
Wearable heart rate, step count, and sleep monitoring device (e.g., OURA™ Ring)		x ^z	x	x	x	x	x	x		x
Previous and concomitant medications ^{aa}	x		x	x	x	x	x	x	x	x
Adverse events ^{bb}	x	x	x	x	x	x	x	x	x	x
Study drug dispensation ^{cc}			x			x				
Study drug accountability				x	x	x	x	x		x

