Table 1 Schedule of Activities (cont.)

CAPS-5=Clinician-Administered PTSD Scale for Diagnostic and Statistical Manual of Mental Disorders, Version 5; CGI-C=Clinician Global Impression of Change; CGI-S=Clinician-Global Impression of Severity; CPK=creatine phosphokinase; CK-MB=creatine kinase-MB; CPFQ=Cognitive and Physical Functioning Questionnaire; C-SSRS=Columbia-Suicide Severity Rating Scale; cTnl=cardiac troponin; DSM-5=Diagnostic and Statistical Manual of Mental Disorders, Version 5; eCRF=electronic Case Report Form; EEG=electroencephalogram; HBcAb=hepatitis B core antibody; HBsAg=hepatitis B surface antigen; HCV=hepatitis C virus; HDL=high-density lipoprotein; hs-cTnT=high-sensitivity-cardiac troponin T; LDH=lactate dehydrogenase; LDL=low-density lipoprotein; LEC-5=Life Events Checklist for DSM-5; PCL-5=PTSD Checklist for DSM-5; PCP=phencyclidine; PGI-C=Patient Global Impression of Change; PGI-S=Patient Global Impression of Severity; PHQ-9=Patient Health Questionnaire-9; PK=pharmacokinetic; PTSD=post-traumatic stress disorder; QTc=corrected QT interval; Pre-Rand=randomization; SCID-5=Structured-Clinical Interview for DSM-5; SDS=Sheehan Disability Scale; RBR=Research Biosample Repository; UV=unscheduled visit; ULN=upper limit of normal; WGS=whole genome sequencing.

Notes: On treatment days, all assessments should be performed prior to dosing, unless otherwise specified.

The visit window is ± 3 days, and all assessments should be completed within the visit window. *Following any visit that may occur outside of allowable visit window*, participants should return to the initial planned schedule (per randomization *as Day 1*) for all subsequent visits. For participants who terminate early, assessments listed under the early discontinuation visit should be completed. For safety follow up, the visit window is $-3/+7$ days and all safety assessments should be completed within the visit window.

Unscheduled visits may be performed if clinically indicated. The following assessments should be performed at a minimum: concomitant medications, adverse events, and vital signs. Additional safety assessments may be performed as clinically indicated, per investigator discretion.

- ^a A safety follow-up visit must occur for all participants at 2 weeks following their last study treatment dose.
- ^b To be conducted if a participant discontinues from the study or study-drug treatment prematurely.

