- ^{aa} Concomitant therapy includes any medication (e.g., prescription drugs, over-the-counter drugs, approved dietary and herbal supplements, nutritional supplements, and any non medicinal interventions, such as individual psychotherapy, smoking cessation therapy, and rehabilitative therapy) used by a participant 24 weeks prior to screening until the follow-up visit.
- ^{bb} After informed consent has been obtained but prior to initiation of study drug, only serious adverse events caused by a protocol-mandated intervention should be reported. The investigator is not required to actively monitor participants for adverse events after the end of the adverse event reporting period (defined as 2 weeks after the final dose of study drug). However, the Sponsor should be notified if the investigator becomes aware of any serious adverse event that occurs after the end of the adverse event reporting period if the event is believed to be related to prior study drug treatment. Every effort should be made to follow all serious adverse events considered to be related to study drug or trial-related procedures until a final outcome can be reported.
- ^{cc} Participants should be instructed to take their medication at home at the same time each day, preferably in the morning. At study visits, they should take the study drug once all assessments are completed, except for Week 6. Study drug dispensation can take place at any time during the visit. *Participants who need to take their medication at a time of day outside of their normal routine may do so, but only one dose may be taken each day. If a dose is missed for that day, the participant should make a note to report this missed dose to the site at their next telephone or site visit.*

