4.1.3 Follow-Up Period

A safety follow-up visit will take place 2 weeks after the participant's Week 12 visit or 2 weeks after last dose to assess whether any adverse events have occurred following the end of treatment.

A study schema is provided in Section 1.2 (see Figure 1). A schedule of activities is provided in Section 1.3 (see Table 1).

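### The safety follow-up visit may be held up to 3 days before the 14-day adverse event reporting period ends, and Section 8.3.1 gives two end points without saying which governs

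*Combined protocol and SAP*

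**What the plan says.** **Visit timing.** Table 1 footnote a (Section 1.3) states: "A safety follow-up visit must occur for all participants at 2 weeks following their last study treatment dose". Section 4.1.3 counts from the Week 12 visit or from the last dose and gives the purpose of the visit: "2 weeks after last dose to assess whether any adverse events have occurred following the end of treatment". The Table 1 notes add: "For safety follow up, the visit window is $-3/+7$ days". The study-day row reads "Study Day(s) -28 to -1 -7 to -1 1 14 28 42 63 84 98", which puts Week 12 on Day 84 and the safety follow-up on Day 98. For the treatment visits, "The visit window is ± 3 days, and all assessments should be completed within the visit window". The synopsis has study drug given at the Week 12 visit once assessments are done, so for a completer the last dose falls on the day of that visit.

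**Reporting period.** Section 8.3.1: "All adverse events will be reported from the start of treatment until 14 days after final study drug or until the last follow-up visit". Footnote bb: "the end of the adverse event reporting period (defined as 2 weeks after the final dose of study drug". A3-5.2 ends reporting of serious adverse events (SAEs) and adverse events of special interest (AESIs) at 14 days after the final dose. A3-6 defines the adverse event reporting period as those same 14 days; beyond it, only SAEs believed related to study treatment are to be notified. A3-3.4.1 (documenting resolution) and A3-7.7 (deaths) take the period from Section 8.3.1 instead.

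**End of participation.** Under Section 4.4, completing the last visit in the schedule completes the study. Table 1 shows no later visit or call.

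**The concern.** The follow-up visit exists to capture what happens in the two weeks after treatment, yet its window lets it take place before those two weeks are over. When it does, the remaining days have no scheduled contact in which events would be asked about.

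The duty to look for events in those days is also unclear. Footnote bb releases the investigator from active monitoring only once the two weeks are over. Section 8.3.1 releases the investigator when participation ends, which for a completer is the follow-up visit.

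A late visit raises the opposite problem. An event after day 14 but before or at the visit is inside the period on one reading of Section 8.3.1 and outside it under footnote bb and A3-6. The analysis does not settle this: Section 9.4.5 summarizes events from the first dose onward with no upper limit. Which late events are tabulated therefore depends on when the visit was scheduled and which section the site followed.

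**Working it through.** **Inputs.** Week 12: Day 84 ±3, i.e. Days 81 to 87 (Table 1 and notes). Safety follow-up: Day 98 in the table row, 2 weeks after last dose in footnote a, window -3/+7 (notes). Reporting period: 14 days after last dose (footnote bb, A3-5.2, A3-6). Last dose: day of the Week 12 visit (synopsis).

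**The plan's own figure.** Nominal gap = 98 − 84 = 14 days. The two weeks reproduce when both visits are on their nominal days.

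**Counting from the last dose (footnote a).**
- Earliest visit: 14 − 3 = day 11. Latest: 14 + 7 = day 21.
- Days of the period after the last scheduled contact: 14 − 11 = 3, and 3/14 = 21%.
- Of the 11 permitted visit days (11 to 21), three (11, 12 and 13) fall before the period ends.
- Days beyond the period when the visit is latest: 21 − 14 = 7 (days 15 to 21).

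**Counting from Day 98 (the printed study day).** Follow-up may fall on Days 95 to 105.
- Earliest: 95 − 87 = 8 days after last dose, leaving 14 − 8 = 6 days uncovered (6/14 = 43%).
- Latest: 105 − 81 = 24 days, i.e. 24 − 14 = 10 days beyond the period.
- Of the 7 × 11 = 77 permitted pairs of visit days, 21 give a gap under 14 days. This is a count of pairs, not a probability; the documents say nothing about how visits will be distributed.

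**What the two end points in 8.3.1 do.**

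| Visit on day after last dose | End under 14-day rule | End under visit rule |
|---|---|---|
| 11 | 14 | 11 |
| 14 | 14 | 14 |
| 21 | 14 | 21 |

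They agree only on day 14. As an example, take a visit due on day 21 and a death on day 18 judged unrelated. A3-7.7 requires deaths within the 8.3.1 period to be recorded regardless of relationship, so this death is reportable if the visit rule governs. Under A3-6 the period closed on day 14 and the event is not a related SAE, so it is not reportable.

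**Scale.** With 15 participants planned per arm (Section 9.2), one participant's event counted or not moves an arm's incidence by 1/15 = 6.7 percentage points.

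**With a 0/+7 window from the last dose.** Earliest visit: day 14. Uncovered days: 14 − 14 = 0.

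**The case against.** Several stronger readings are tempting, and the documents do not support them.

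- *The visit can be as early as day 8 or as late as day 24.* A reader might take this from Table 1. It requires the visit to be fixed to Day 98 whatever the date of the last dose. Footnote a and Sections 4.1 and 4.1.3 all count from the last dose or the Week 12 visit. The note returning participants to the Day 1 schedule applies only after a visit outside its window, and a Week 12 visit on Day 87 is inside it. The wider range is a possible misreading by sites, not the plan's evident intention.
- *Events after an early visit are lost.* Only scheduled contact is missing. Spontaneous reports and unscheduled visits remain possible, footnote bb implies monitoring up to day 14, and related SAEs stay reportable afterwards. Participants who stop treatment early are asked back at Week 12 (Sections 7.1 and 9.4.2), which may come after their safety follow-up, so the gap concerns completers.
- *Appendix 3 excludes all events after day 14.* A3-5.2 covers only SAEs and AESIs. For other adverse events the competing texts are footnote bb and A3-6.
- *The safety comparison is biased.* Adverse event incidence is one of several listed safety endpoints, and none is named as the main one. The same window applies to both blinded arms, the analysis is descriptive, and most of the follow-up safety checks are also done at Week 12.

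These objections limit the size of the problem. They do not remove the -3 days, which let the visit precede the end of the period on any anchor, or the unresolved alternative in Section 8.3.1.

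**Conclusion.** The point holds as a low-cost improvement. For completers, the last scheduled contact may come on day 11 after the last dose, leaving up to 3 of the 14 reporting days (21%) without one. If the visit is late, up to 7 further days are in or out of the period depending on the section used, for events other than related SAEs. These figures assume that the visit is counted from the last dose, that the last dose is taken at the Week 12 visit, and that the visit is held within its window. The 8-to-24-day range applies only if sites work from Day 98; that possibility is a reason to state the anchor, not a finding in itself.

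The consequence is a few days of adverse event ascertainment in about 30 participants. Efficacy endpoints are unaffected, and nothing in the documents shows a difference between arms.

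**What to change.** 1. In Table 1 and its notes, set the safety follow-up window to 0/+7 days counted from the actual last dose (days 14 to 21), and mark Day 98 as nominal only.
2. State one reporting end in Section 8.3.1, footnote bb, A3-5.2 and A3-6: the later of 14 days after the last dose and the safety follow-up visit. If no visit takes place, this is day 14. The pointer in A3-5.2 to events more than 14 days after the final dose should change with it. A3-3.4.1 and A3-7.7 refer to 8.3.1 and need no separate edit.

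**Cost.** Amendment wording and visit-window settings. The window shrinks from 11 to 8 permitted days, three fewer for scheduling, and no visit is added. Under the later-of rule, participants seen within the window have 14 to 21 days of post-treatment collection. If a common length is wanted for the tables, events can be cut at day 14 by onset date, provided the report says so.

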8.3.2 Method of Detecting Adverse Events and Serious Adverse Events

The method of recording, evaluating, and assessing causality of adverse events and serious adverse events and the procedures for completing and transmitting serious adverse event reports are provided in [Appendix 3](#).

Care will be taken not to introduce bias when detecting adverse events and/or serious adverse events. Open-ended and non-leading verbal questioning of the participant is the preferred method to inquire about adverse event occurrences.

8.3.3 Follow-Up of Adverse Events and Serious Adverse Events

After the initial adverse event or serious adverse event report, the investigator is required to proactively follow each participant at subsequent visits or contacts. All

adverse events will be followed until the event has resolved to baseline grade or better, the event is assessed as stable by the investigator, the participant is lost to follow-up (as defined in Section 7.3), or the participant withdraws consent. Further information on follow-up procedures is provided in [Appendix 3](#).

